6.2.5.2 Solicited Local and Systemic Reactogenicity Symptoms

All subjects will record solicited local and systemic reactions and other unsolicited symptoms/complaints, including start and stop dates, on an 8-day diary card following each vaccination. The investigator or his/her designee will review the information from the diary card or from memory with the subject at each visit and grade reactogenicity using a standard toxicity grade (Appendix 3, Section 12.3). The diary card will be collected from the subjects and stored as a source document.

- Solicited local reactions at the injection site will include erythema/redness, induration/swelling, and pain.
- Solicited systemic reactions will include fever, myalgia, arthralgia, fatigue, headache, nausea, vomiting, diarrhea, and chills.

The above solicited local and systemic reactions will be recorded including start and stop dates, worst daily grade, any treatment required, and action taken. The investigator will assess if solicited local and systemic reactions will be considered as related to IP according to Section 6.2.5.6. The severity of local and systemic reactions will be graded using the FDA Toxicity Grading Scale for Healthy Adult and Adolescent Volunteers Enrolled in Preventive Vaccine Clinical Trials (Appendix 3, Section 12.3).

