cited AEs ^a	Days 1-21 Post each vaccination
IAAEs, and MMCs	Entire Study Period ^b
gnancies	Entire Study Period ^c
	of Event ited AEs bited AEs ^a IAAEs, and MMCs nancies

Table 4-1Safety Data Reporting Periods

Abbreviations: AE, adverse event; MAAE, medically attended adverse event; PIMMC, potentially immune-mediated medical condition; SAE, serious adverse event.

^a Unsolicited AEs will be collected through the end of the study visit window for each AE collection period (i.e., 21 days after each vaccination ± 3 -Day window = 21 ± 3 days).

^b The entire study period is from the time a subject receives the first study injection through the end-of-study visit. If the investigator becomes aware of any related SAE or related MAAE after exit from or completion of the study, he or she is obligated to report this event.

^c Pregnancies that occur during a subject's participation in the study will be followed until resolution and 2 weeks after live birth even if the pregnancy ends after the end-of-study visit.

Subject Grouping in Data Listings

In general, subjects will be grouped or sorted with other subjects who belong to the same study group as treated. However, in the event that a subject incorrectly receives doses of IP different from group A-L regimen, the subject will be grouped or sorted in separate categories based on actual vaccines received.

Missing Data

Missing data will not be imputed unless otherwise specified.

Adverse events and concomitant medications with missing start dates will have their start dates imputed.

If a start date is completely missing, then the first dose date of IP will be used.

If both Day and month are missing but year is available (--/---/YYYY), then the date will be imputed as follows:

- If the year is less than the year the IPs were administered, then the start date will be imputed as Jul 1st.
- If the year is equal to the year the IPs were administered, then the start date will be imputed as the first dose date of IP.
- If the year is greater than the year the IPs were administered, then Jan 1st of the year will be used.

If only Day is missing (--/MMM/YYYY), then the following rules will be applied relative to the year that the IPs were given:

- If the year is equal to the year that the IPs were administered, then
 - If the start month is equal to the month that the first dose of IP was administered, then the first dose date of IP will be used.

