4.3.3 Safety Set

The safety set will consist of all subjects who are randomly assigned and receive at least 1 dose of IP. Safety endpoint summaries and listings will be performed on the safety set using study group treatment actually received.

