All AEs reported after the first dose of IP will be summarized in tables. AEs within 21 days of each dose of IP, and before the date and time of the next dose of IP (if applicable) will be summarized in tables based on each dose only (Dose 1, 2 for Groups A-D, G-J; Dose 1, 2, 3 for Group E, F, K and L). When the time of an AE is missing and the AE start date is on the date of vaccination, then that AE will be considered as happening after the corresponding dose of IP.

All AEs will be summarized by presenting the number and percentage of subjects having any AEs and having each individual adverse event based on SOC and PT, and PT only. At each level of subject summarization, a subject is counted once if the subject reported one or more events. Percentages will be calculated out of the number of subjects as treated per study group in the Safety Set. For the dose-specific AE summaries, percentages will be calculated out of the number of subjects as treated per study group corresponding to Dose 1, Dose 2 or Dose 3.

Unless otherwise stated, AEs will be sorted in descending order by frequency of SOC and PT.

The following summaries, based on Dose 1 only, Dose 2 only, and both Dose 1 and Dose 2 for Groups A-D, G-J and Dose 1 only, Dose 2 only, Dose 3 only, and all Dose 1, Dose 2 and Dose 3 for Groups E, F, K and L will be provided:

- Overview summary of the number and percentage of subjects with any AE, SAE, AE related to IP, AE leading to study withdrawal, AE leading to death, solicited local AE, severe solicited local AE, solicited systemic AE, severe solicited systemic AE, MAAE, PIMMC, unsolicited AE, severe unsolicited AE, and unsolicited AE related to IP
- All AEs by SOC and PT
- All AEs by AE Type and PT
- All AEs by SOC, PT and Severity

- All AEs by SOC, PT and Relationship
- All unsolicited AEs by SOC, PT and Day of Onset

The following summaries with 95% exact CIs using Clopper Pearson method, based on events recorded during the 8 days post each vaccination will be provided as the analysis of primary safety endpoint:

- Solicited Local AEs by Severity
- Solicited Systemic AEs by Severity

All MAAEs and PIMMCs after the first dose of IP will be summarized in a table by SOC, PT and Severity.

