In all by-severity summaries, the severity that will be presented represents the greatest severity captured in the eCRF if a subject reported multiple occurrences of the same AE. The possible severities include "Mild", "Moderate" and "Severe". The missing severity will be imputed as "Severe".

In all by-relationship summaries, the relationship that will be presented represents the greatest relatedness captured in the eCRF if a subject reported multiple occurrences of the same AE. The possible relationship includes "Related" and "Unrelated". The missing relationship will be imputed as "Related".

All AEs will be included in a data listing containing all subject-level data collected in the eCRF. All SAEs, all AEs leading to study withdrawal, MAAEs, PIMMCs and severe AEs will be listed separately.

A listing of SAEs and MAAEs, including a subset of specific PIMMCs for 12 months after the last dose of study vaccine will be presented in the addendum to the CSR once the study is complete.

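### Solicited-reaction percentages are divided by everyone given the dose, so subjects with no solicited follow-up count as non-reactors and pull the primary safety rates down to the extent such subjects exist

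*SAP*

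**What the plan says.** SAP Section 9.1 gives two denominators for adverse event summaries. The general rule is "Percentages will be calculated out of the number of subjects as treated per study group in the Safety Set". For dose-specific summaries, "percentages will be calculated out of the number of subjects as treated per study group corresponding to Dose 1, Dose 2 or Dose 3".

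The primary safety analysis comes later in the same section: "The following summaries with 95% exact CIs using Clopper Pearson method, based on events recorded during the 8 days post each vaccination". It covers local and systemic solicited events by severity and names no denominator of its own. SAP Section 4.3.3 defines the population: "The safety set will consist of all subjects who are randomly assigned and receive at least 1 dose of IP". Neither section requires any solicited data to be present.

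Two missing-data rules are relevant. SAP Section 4, under Missing Data, says "Missing data will not be imputed unless otherwise specified". SAP Section 9.1 adds, for recorded events, "The missing severity will be imputed as" Severe.

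On data capture, Protocol Section 6.2.5.2 says "All subjects will record solicited local and systemic reactions and other unsolicited symptoms/complaints, including start and stop dates, on an 8-day diary card". The same section lets the investigator or a designee work without the card: they "will review the information from the diary card or from memory with the subject at each visit". Protocol Section 6.2.2 has subjects monitored for solicited events for at least 30 minutes after vaccination. Protocol Tables 12–1 and 12–2 schedule a telephone call 3 days after each dose and a visit 7 days after.

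**The concern.** The numerator counts recorded events and the denominator counts people who were injected. A dosed subject with no solicited information after leaving the clinic, and no reaction noted before leaving, stays in the denominator and cannot enter the numerator. In the table that subject looks the same as one who was followed for 8 days and had no reaction.

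This affects the primary safety endpoint, whose main output is a percentage and an exact interval for each group. The reader also cannot see or correct the dilution. The planned disposition summary reports Day 142 or Day 262 completion and treatment by dose, and the exposure summary reports doses received. Neither counts dosed subjects without solicited data. If the share without data differed by group or dose, the side-by-side rates would be diluted unequally.

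The plan handles its other primary endpoint differently. The immunogenicity sets admit only subjects with a valid, determinate post-vaccination result (SAP Sections 4.3.4 and 4.3.5).

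**Working it through.** **1. The plan's own figure.** SAP Table 4-2 (Protocol Table 7–1) gives the probability of seeing at least one event, including a Grade 3 solicited event. The formula is 1 − (1 − p)^n. For n = 60 and p = 1%, 2% and 5% it gives 45.28%, 70.24% and 95.39%, against the stated 45.3, 70.2 and 95.4. All 14 cells reproduce. The table assumes that all 60 subjects are observed. At p = 5%, with 57, 54 or 48 observed, 95.4% becomes 94.6%, 93.7% or 91.5%. The table does not depend on the denominator rule, so reproducing it neither supports nor weakens the point.

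**2. Inputs for the dilution.** Group size is 60 (SAP Section 4.1). Let p be the true reaction rate. Let m be the share of dosed subjects with no solicited information after the 30-minute observation and no reaction recorded by then. The documents give neither p nor m, so every value of both below is an assumption.

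**3. Formula.** If missingness is unrelated to reaction, the expected rate over all dosed subjects is p(1 − m). The absolute shortfall is p × m and the relative shortfall is m.

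| True rate p | m = 0 | m = 2% | m = 5% | m = 10% | m = 20% |
|---|---|---|---|---|---|
| 80% | 80% | 78.4% | 76% | 72% | 64% |
| 50% | 50% | 49% | 47.5% | 45% | 40% |
| 5% | 5% | 4.9% | 4.75% | 4.5% | 4% |

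**4. Effect on the Clopper-Pearson interval.** Three illustrations, each with 60 dosed:

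- 6 without data, 27 reacting: 27/60 = 45.0% (32.1 to 58.4) against 27/54 = 50.0% (36.1 to 63.9).
- 6 without data, 43 reacting: 43/60 = 71.7% (58.6 to 82.5) against 43/54 = 79.6% (66.5 to 89.4).
- 1 without data, 47 reacting: 47/60 = 78.3% (65.8 to 87.9) against 47/59 = 79.7% (67.2 to 89.0).

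The whole interval moves down. Its width changes little, and the direction depends on the rate. Over all dosed subjects it is 26.3 points wide against 27.8 in the first case, but 23.9 against 22.9 in the second.

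**5. Which denominator applies.** The primary summaries concern the 8 days after each vaccination, so the dose-specific denominator is the natural reading, though the SAP does not say so. On that reading, subjects who never received a dose are already out of that dose's denominator. Under the general rule they would stay in.

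**The case against.** The strongest reply is that a missing diary is not missing data. Reactions can be taken from memory at visits, noted in the 30-minute observation or raised at the 3-day call, and solicited events go on the AE page (Protocol Section 6.2.5.5). A subject who reports a reaction by any of these routes enters the numerator without ever returning a card. This stands: m is smaller than the diary-loss rate, perhaps much smaller. It does not repair the rule, because recall needs a later contact and 30 minutes of observation cannot cover the remaining days.

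Second, the study is descriptive, with no formal testing. One subject in 60 moves an 80% rate by less than 2 points, inside an interval about 22 points wide. That also stands, for small m.

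Third, restricting to subjects with data recovers the true rate only if missingness is unrelated to reaction. If non-reactors are the ones who fail to report, the restricted rate is too high. This is correct, and is the reason to show both rates.

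Four stronger readings are tempting and are not supported:

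- A reader might infer that every subject without a diary is scored reaction-free. The recall and observation routes rule that out.
- A reader might infer that the rates are certainly understated. No missing rate is given, and the shortfall could be zero.
- A reader might infer a contradiction with the no-imputation rule. Dividing recorded events by exposed subjects fills in no value. The effect resembles imputing no reaction, so there is tension with the rule but no breach of it.
- A reader might infer special harm at the Day 142 dose. The dose-specific denominator already drops subjects not given that dose, and the documents give no evidence of differential loss among those who were.

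Setting missing severity to Severe is not an offset, since it acts only on events already recorded.

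**Conclusion.** The point holds in conditional form. SAP Section 9.1 states a denominator that does not depend on follow-up, so dosed subjects with no solicited information after the 30-minute observation are counted as non-reactors. The primary safety rates and their exact intervals are lowered by the factor (1 − m). At an assumed true rate of 80%, that is 1.6, 4 or 8 points for m of 2%, 5% or 10%. At a true rate of 5% and m of 10%, it is 0.5 point. These sizes assume that missingness is unrelated to reaction. If it is related, neither denominator is unbiased. The effect is zero if every dosed subject has solicited data, and as planned the report would not show which case applies. The change is worth making because it is cheap and concerns a primary endpoint.

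**What to change.** In SAP Section 9.1, give the primary solicited summaries their own denominator for each dose: Safety Set subjects who received that dose and have at least one solicited assessment in the 8-day period, from the diary or from call or visit recall. Any recorded solicited reaction qualifies a subject. The 30-minute observation without a reaction should not qualify on its own, since it is scheduled for everyone vaccinated and would leave the denominator essentially unchanged.

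Report the number of dosed subjects without solicited data by group and dose beside each rate. Keep the all-dosed denominator as a sensitivity analysis for solicited reactions and as the denominator for unsolicited events.

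The cost is SAP wording, one flag per dose and one count column. The downside is a slightly smaller n and slightly higher reported rates. Intervals will be slightly wider at low and middle rates, though not necessarily at high ones. A subject with only one completed diary day would still count as observed, so partial diaries remain a smaller source of dilution.

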3.1 Study Design

This is a randomized, double-blinded, Phase 2 study to assess the safety and immunogenicity of a homologous or heterologous prime-boost or prime-prime-boost series with inactivated monovalent influenza H5 vaccines stored in the NPIVS, administered IM with either AS03 or MF59 adjuvant in healthy males and nonpregnant females, aged 18 to 49 years, inclusive.

Screening will occur within a 14-day period before randomization. Approximately 720 subjects will be equally and randomly assigned to one of 12 study groups within each site. Study staff not involved in investigational product (IP) preparation and administration will be blinded to unique group assignment. Two doses of adjuvanted vaccine separated by 21 days (Groups A-D, G-J) or 2 doses of adjuvanted vaccine separated by 21 days followed by a third dose of adjuvanted vaccine 120 days following the second dose (Groups E, F, K, L) will include HA antigen from the NPIVS.

Investigational product treatment arms are detailed in Table 3–1.

Protocol: BP-I-16-005 Version 2.0

26 February 2018

Table 3–1Treatment Arms					
Study Group	Dose #1 (Day 1) Strain Details (Manufacturer)	Dose #2 (Day 22) Strain Details (Manufacturer)	Dose #3 (Day 142) Strain Details (Manufacturer)	Adjuvant	
А	A/Vietnam/1203/2004 H5N1 (Sanofi Pasteur)				
В	A/Indonesia/05/2005 H5N1 (Sanofi Pasteur) A/gyrfalcon/Washington/41088-6/2014 H5N8		3		
С	A/duck/Bangladesh/19097/2013 H5N1 (Seqirus)	(Seqirus)	N/A		
D	A/gyrfalcon/Washington/41088-6/2014 H5N8 (Seqirus)	\sim $\Delta / Indonesia/Up/ / UUp Hp/N L (Nanoti Pastellir)$			
Е	A/duck/Bangladesh/19097/2013 H5N1 (Seqirus)	rus) (Seqirus) (H5N1) (Sanofi Pasteur) n/41088-6/2014 H5N8 A/gyrfalcon/Washington/41088-6/2014 H5N8 A/barheaded goose/Qinghai Lake/1A/2005			
F	A/gyrfalcon/Washington/41088-6/2014 H5N8 (Seqirus)				
G	A/Vietnam/1203/2004 H5N1 (Sanofi Pasteur)				
Н	A/Indonesia/05/2005 H5N1 (Sanofi Pasteur) A/gyrfalcon/Washington/41088-6/2014 H5				
Ι	A/duck/Bangladesh/19097/2013 H5N1 (Seqirus)	(Seqirus)	N/A	MF59	
J	A/gyrfalcon/Washington/41088-6/2014 H5N8 (Seqirus)	A/Indonesia/05/2005 H5N1 (Sanofi Pasteur)			
K	A/duck/Bangladesh/19097/2013 H5N1 (Seqirus)	A/duck/Bangladesh/19097/2013 H5N1 (Seqirus)	A/barheaded goose/Qinghai Lake/1A/2005 (H5N1) (Sanofi Pasteur)		
L	A/gyrfalcon/Washington/41088-6/2014 H5N8 (Seqirus)	A/gyrfalcon/Washington/41088-6/2014 H5N8 (Seqirus)	A/barheaded goose/Qinghai Lake/1A/2005 (H5N1) (Sanofi Pasteur)		

Abbreviation: N/A, not applicable.

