5.1 Method of Assigning Subjects to Treatment Groups

Subjects will be randomly assigned to 1 of 12 study groups stratified by site. An IRT will be used to administer the randomization schedule centrally. Biostatistics will generate the randomization schedule using SAS[®] software Version 9.3 or later (SAS Institute Inc, Cary, North Carolina) for IRT, which will link sequential subject randomization numbers to treatment codes. The randomization schedule will be created by the dedicated randomization team, stored in a separate project area, and will be blinded to the project team.

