7.4 Sample Size Calculations

Approximately 720 subjects with 60 subjects per study group will be enrolled in the study. Approximately half of enrolled subjects will be selected to provide a blood sample for PBMC collection.

The number of subjects proposed to be enrolled in this protocol is based upon previous experience with similar studies such as the Mix and Match Studies (NCT 01317745 and NCT 01217758) performed by Division of Microbiology and Infectious Diseases/National Institute of Allergy and Infectious Diseases. These prior studies had study groups of similar size that proved to be sufficient to allow the collection of meaningful data, especially with respect to acute solicited AEs and antibody results. While the current study is not designed to test specific hypotheses, Table 7–1 and Table 7–2 indicate the power of the proposed sample size to detect a range of common, immediate postvaccination elicited safety events as well as to meet the success criteria for SPR.

26 February 2018

Protocol: BP-I-16-005 Version 2.0

Table 7–1	Safety – Power for Detecting at Least 1 SAE, MAAE, or a Grade 3
	Safety – I ower for Detecting at Least I SAE, MAAE, or a Grade 5
	Solicited AE

True Event Rate (%)	Power (%) N = 60	Power (%) N = 120
0.1	5.8	11.3
0.5	26.0	45.2
1	45.3	70.1
2	70.2	91.2
3	83.9	97.4
4	91.4	99.3
5	95.4	99.8

Abbreviations: AE, adverse event; MAAE, medically attended adverse event; SAE, serious adverse event. Note: The exact method was used for the calculations in this table.

Note: Serious adverse events and MAAEs will be collected for approximately 12 months after the last study vaccine dose. Note: Solicited AEs will be collected for 7 days after each of the vaccine doses.

Table 7–2	Immunogenicity – Power for Meeting Success Criteria of SPR
-----------	--

Success Criteria (%)	Proportion of Subjects Achieving a Serum HAI Antibody Titer of at Least 1:40 for the Testing Vaccine (%)	Power (%) N = 60	Power (%) N = 120
	90	98.5	>99.9
70	85	81.9	99.0
	80	44.9	79.0

Abbreviations: HAI, hemagglutination inhibition; SPR, seroprotection rate.

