7.7.3 Analysis of Primary Endpoints

7.7.3.1 Analysis of Primary Safety Endpoint

Solicited local and systemic reactions (recorded as AEs, Section 6.2.5.2) during the 8 days after each vaccination, inclusive of the vaccination day, will be summarized as a frequency table that includes 95% exact CIs by study group and by the degree of severity (mild, moderate, or severe).

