12.1 Appendix 1: Schedule of Events

H5 Influenza Vaccine With Either AS03 or MF59

Protocol: BP-I-16-005 Version 2.0

26 February 2018

Table 12–1Schedule of Events, Groups A to D, G to J

Study visit	Screening	V1	V2 ^a	V3	V4	V5 ^a	V6	V7	V8	V9 ^a (EOS)	ET	Unsch
Study day	-14 to -3	1	4	8	22	25	29	43	142	387	N/A	N/A
Window allowance (days)			V1+3 (±1)	V1+7 (±1)	V1+21 (+3)	V4+3 (±1)	V4+7 (±1)	V4+21 (±3)	V1+141 (±7)	V1+386 (±7)	N/A	N/A
Obtain informed consent	Xb											
Vital sign measurements ^c	Х	Х		Х	Х		Х	Х			Х	X ^d
Height and weight	Х	Xe										
Medical history	Х	Xe										
Perform subject interview ^f			Х	Х	Х	Х	Х	Х	Х	Х	Х	Х
Review diary card ^g			Х	Х	Х	Х	Х	Х			X ^h	X ^h
Distribute diary card ^g and review instructions		X DCI		X DCII	X DCIII		X DCIV					
Distribute measuring tool and thermometer and review instructions		Х			Х							
Collect diary card ^g				X DCI	X DCII		X DCIII	X DCIV				
Concomitant medications	X ⁱ	X ^{e,i}	Х	Xj	Xe	Х	Xj	Х	Х	Х	Х	Х
Concomitant vaccinations	X ⁱ	X ^{e,i}	Х	Xj	Xe	Х	Xj	Х	Х	Х	Х	Х
Complete physical examination ^k	Х											
Targeted physical examination ¹		Xe		Х	Xe		Х				Xď	X ^d
Urine pregnancy test (WOCBP)	Х	X ^{e,m}			X ^{e,m}							X ^d
Review inclusion and exclusion criteria	Х	X ^e			X ^e							

Protocol: BP-I-16-005 Version 2.0

H5 Influenza Vaccine With Either AS03 or MF59

26 February 2018

Study visit	Screening	V1	V2 ^a	V3	V4	V5 ^a	V6	V 7	V8	V9 ^a (EOS)	ЕТ	Unsch
Study day	-14 to -3	1	4	8	22	25	29	43	142	387	N/A	N/A
Window allowance (days)			V1+3 (±1)	V1+7 (±1)	V1+21 (+3)	V4+3 (±1)	V4+7 (±1)	V4+21 (±3)	V1+141 (±7)	V1+386 (±7)	N/A	N/A
Venous blood sample collection for clinical safety laboratory tests ⁿ	Х			X°	X ^{e,o}		Xº					X ^d
Venous blood sample collection for antibody assays		Xe			Xe			Х	Х			
Cellular immunology (subset only)		Xe			Xe			Х	Х			
Randomization		X ^e										
Vaccination		Х			Xp							
Monitor subject for 30 minutes following vaccination ^q		Х			Х							
Examine vaccination site ^r		X ^s		Х	X ^s		Х				Xď	Xt
AE/MAAE/PIMMC/SAE assessment ^u		Х	Х	Х	Х	Х	Х	Х	X	Х	Х	Х

Table 12–1Schedule of Events, Groups A to D, G to J

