8.2 Secondary Analysis

- Geometric mean titers (GMTs) of HAI antibody responses against each strain vaccinated at Day 1, 22, 43, and 142 visits (Groups A-D, G-J) and Day 1, 22, 43, 142, 163 and 262 visits (Groups E, F, K and L) and asymptotic 95% CIs will be summarized along with other descriptive statistics, including number of subjects, geometric standard deviation, minimum, maximum, and median for each treatment group. Line plots will be provided for GMT of HAI and corresponding 95% CI for all visits.
- GMTs of MN antibody responses against each strain vaccinated at Day 1, 22, 43, and 142 visits (Groups A-D, G-J) or Day 1, 22, 43, 142, 163 and 262 visits (Groups E, F, K and L) and asymptotic 95% CIs will be summarized along with other descriptive statistics, including number of subjects, geometric standard deviation, minimum, maximum, and median for each treatment group. Line plots will be provided for GMT of MN and corresponding 95% CI for all visits.
- SPR for HAI antibody responses against each strain vaccinated at Day 1, 22, 43, and 142 visits (Groups A-D, G-J) or Day 1, 22, 43, 142, 163 and 262 visits (Groups E, F, K and L) along with asymptotic 95% CIs will be summarized. SPR for the combinations of HAI antibody responses against multiple strains vaccinated will be also summarized for each treatment group. Line plots will be provided for SPR for HAI and corresponding 95% CI for all visits.
- SCR for HAI antibody responses against each strain vaccinated at Day 22, 43, and 142 visits (Groups A-D, G-J) or Day 22, 43, 142, 163 and 262 visits (Groups E, F, K and L) with asymptotic 95% CIs will be summarized for each treatment group. Line plots will be provided for SCR for HAI and corresponding 95% CI for all visits.
- SCR for MN antibody responses against each strain vaccinated at Day 22, 43, and 142 visits (Groups A-D, G-J) or Day 22, 43, 142, 163 and 262 visits (Groups E, F, K and L) with asymptotic 95% CIs will be summarized for each treatment group. Line plots will be provided for SCR for MN and corresponding 95% CI for all visits.

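### Groups C/E, D/F, I/K and J/L share the same dose 1, but no pooled dose-1 or Day 22 summary is planned, so precision is lost on about 120 subjects per exposure

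*SAP*

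**What the plan says.** Protocol 3.1, Table 3-1 (repeated as SAP Table 3-1) sets out the paired groups as follows:

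| Dose 1 | Groups | Dose 2 (Day 22) |
|---|---|---|
| dk/BANG + AS03 | C, E | gf/WA in C, dk/BANG in E |
| gf/WA + AS03 | D, F | IN in D, gf/WA in F |
| dk/BANG + MF59 | I, K | gf/WA in I, dk/BANG in K |
| gf/WA + MF59 | J, L | IN in J, gf/WA in L |

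On allocation, Protocol 5.1 states "Subjects will be randomly assigned to 1 of 12 study groups stratified by site", and on size, Protocol 7.4 states "Approximately 720 subjects with 60 subjects per study group will be enrolled in the study". In both schedules of events (Protocol 12.1, Tables 12-1 and 12-2) the Visit 4 entry in the row "Venous blood sample collection for antibody assays" is flagged as taken before vaccination.

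For the primary safety endpoint, Protocol 7.7.3.1 says that solicited reactions after each vaccination "will be summarized as a frequency table that includes 95% exact CIs by study group and by the degree of severity". SAP 9.1 introduces the overview and SOC/PT adverse event tables with "The following summaries, based on Dose 1 only, Dose 2 only". A separate, later sentence covers the Clopper-Pearson tables that form the primary safety analysis. Dose-specific percentages use the as-treated study group as denominator. SAP 8.2 summarises Day 22 GMT, SPR and SCR for each treatment group.

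The only cross-group column is an overall column in tables by randomised treatment (SAP 4, Subject Counts in Table Headers). Both documents show power at N = 120 (Protocol Tables 7-1 and 7-2, SAP Tables 4-2 and 4-3), but neither describes an analysis of that size.

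**The concern.** Up to the Day 22 vaccination, the two members of each pair are the same randomised exposure: same antigen, same adjuvant, same visit days, concurrent site-stratified allocation, with subjects and observers blinded. Reporting them only in separate columns of about 60 gives two imprecise estimates of one quantity and never the better one. The quantities matter to the study. Reactions after dose 1 are part of the primary safety objective. The pre-boost Day 22 titre is the direct measure of a single-dose prime, which the Introduction (Protocol 1) names as a question for the trial. At stake is precision, and the chance of seeing uncommon reactions, for four of the eight dose-1 exposures.

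**Working it through.** **Inputs.** Group size 60 (Protocol 7.4); four pairs with a common dose 1 (Table 3-1); two-sided 95% Clopper-Pearson intervals (SAP 9.1). The log10 titre SD is not in the documents, so 0.3 to 0.6 is assumed.

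**Count of exposures.** Four pairs of 2 × 60 = 120, plus A, B, G and H at 60 each: 4 × 120 + 4 × 60 = 720, in 8 distinct dose-1 exposures.

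**The plan's own figures.** Table 7-1 follows from P(at least one event) = 1 − (1 − p)^n. At p = 1%: 1 − 0.99^60 = 45.28% and 1 − 0.99^120 = 70.06%, against 45.3 and 70.1 in the table. All 14 cells reproduce to rounding. The N = 120 column is therefore exactly what a pooled pair would give:

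| True rate | n = 60 | n = 120 |
|---|---|---|
| 0.5% | 26.0% | 45.2% |
| 1% | 45.3% | 70.1% |
| 2% | 70.2% | 91.2% |

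**Zero events.** Upper 95% limit = 1 − 0.025^(1/n): 5.96% at n = 60, 3.03% at n = 120.

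**Clopper-Pearson intervals.**

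| Observed | n = 60 | n = 120 |
|---|---|---|
| 5% | 1.0–13.9% | 1.9–10.6% |
| 10% | 3.8–20.5% | 5.3–16.8% |
| 50% | 36.8–63.2% | 40.7–59.3% |

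At 50% the half-width falls from 13.2 to 9.3 points, and 9.3/13.2 = 0.70, a reduction of about 30%.

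**Day 22 GMT.** The 95% interval is the GMT multiplied and divided by 10^(t × SD/√n), with t on n − 1 degrees of freedom.

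| Assumed log10 SD | n = 60 | n = 120 |
|---|---|---|
| 0.3 | 1.20 | 1.13 |
| 0.6 | 1.43 | 1.28 |

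**Which subjects can be pooled at Day 22.** SAP 8 restricts GMT and SCR to the IPPS. SAP 4.3.5 requires all planned doses. C, D, I and J therefore need dose 2 and an in-window Day 43 sample, while E, F, K and L also need dose 3 in window and a Day 163 sample. Within a pair, two subjects with equally good Day 22 results can be treated differently because of events months later. Pooling the IPPS as defined would mix two selections. It would also give fewer than 120: an assumed loss of 10–20% leaves 108 to 96.

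**The case against.** The strongest reply is that nothing here is wrong. The study is descriptive, no formal testing is planned for the primary and secondary objectives, the per-group estimates are unbiased with valid exact intervals, and no decision rule rests on the width of a dose-1 interval. The primary safety objective concerns 2-dose and 3-dose series, so reporting by regimen follows from it. Both members of a pair share an adjuvant and so appear on the same page (SAP 3.3), where a reader can add the counts. For GMT, the n and geometric SD are reported. All of this stands, and it makes the point one of efficiency. It does not explain why the better estimate should be left to the reader, especially when both documents quote power at N = 120.

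Four stronger readings are tempting, and the documents do not support them.

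- A reader might take the SAP sentence on dose-specific summaries as governing the primary safety tables. It introduces the overview and SOC/PT tables. By-group reporting of the primary endpoint is fixed by Protocol 7.7.3.1.
- A reader might infer that duplicate columns will produce false findings which pooling prevents. The comparisons listed in SAP 8.3 are at Day 43 and Day 163 only, and keeping 12 columns leaves chance differences visible.
- A reader might infer from the N = 120 column that a pooled analysis was intended and then dropped. Neither document says what that column refers to.
- A reader might think that pooling is free. The Day 22 part needs its own analysis set. SPR is partly covered already, since it is also run on the IFAS, which does not depend on later doses.

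**Conclusion.** The point holds as a missed gain in precision. It is not an error or a bias. For four dose-1 exposures the plan reports at about 60 subjects what could be reported at about 120. The gain on dose-1 safety is firm: it uses the SAP's own interval method and the documents' own power figures, and assumes only that enrolment is near plan and that most subjects receive the assigned dose 1. The gain on Day 22 GMT depends on the assumed SD and on how many subjects have a valid sample taken before dose 2. The primary immunogenicity endpoint (Day 43 or Day 163) is untouched, because the pairs have received different vaccines by then. For the same reason, the argument does not extend to Dose 2, all-dose or Day 43 summaries.

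**What to change.** In SAP 9.1, add supplementary pooled columns or tables for C+E, D+F, I+K and J+L to the Dose-1-only solicited tables (with Clopper-Pearson intervals) and the Dose-1-only unsolicited tables. Use the Safety Set, by dose-1 product and adjuvant actually received. Under SAP 4, a subject whose regimen as received matches none of A–L leaves the group columns. A subject with a correct dose 1 and a wrong later dose should still count in the pooled dose-1 column. Keep the 12 group columns.

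In SAP 8.2, add a separate table of pooled Day 22 HAI and MN GMT, HAI SPR, and HAI and MN SCR. Base it on all subjects who received dose 1 and have a valid Day 22 result from a sample taken before dose 2, not on the IPPS. State that Dose 2, all-dose and Day 43 summaries are not pooled.

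In SAP 4.1, say that N = 120 refers to these pooled pairs or, if pooling is declined, what it does refer to.

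The cost is SAP wording, table shells and one extra analysis set; no new data are needed. The pooled Day 22 Ns will not equal the sum of the IPPS group columns, so the table needs a footnote saying why.
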